7.7. Vital Signs

Vital signs (blood pressure [systolic/diastolic], respiratory rate, body temperature, and pulse) will be measured at the time points detailed in Table 3. All abnormal vital signs will be judged by the investigator as belonging to one of the following categories:

- abnormal and not clinically significant
- abnormal and clinically significant

Before blood pressure and pulse are measured, the patient must rest in a supine or semi-erect/seated position for at least 3 minutes. (The same position and arm or leg should be used each time vital signs are measured for a given patient.) Orthostatic blood pressure and pulse will be measured after the patient is in a standing position for at least 3 minutes (for patients who are able to stand). For patients who find standing difficult or do not allow for a reliable blood pressure and pulse measurement, alternative methods to collect orthostatic blood pressure and pulse should be discussed with the medical monitor. For any abnormal vital sign value, the measurement should be repeated as soon as possible. Any vital sign value that is judged by the investigator as clinically significant will be recorded both on the source documentation and the CRF as an adverse event and monitored as described in Section 7.1.2.

7.8. Electrocardiography

A 12-lead ECG will be recorded at the time points detailed in Table 3. All ECGs will be performed after at least 5 minutes rest in a supine or semi-supine position.

The ECG types are defined as follows:

- A “standard ECG” is a “standard” 10-second 12-lead ECG.
- A “summary ECG” is a continuously recorded ECG of longer than 30 seconds. For a “summary ECG,” the minimal recommended duration is 2 minutes or longer, and the preferred duration is 5 minutes (as it provides the most robust result). If a “summary ECG” is less than 2 minutes, data will still be captured and analyzed to the extent possible.

The investigator should review the ECG at screening to determine patient eligibility for the study and subsequent ECGs for the patient’s continuation in the study. All ECGs should be reviewed by the investigator for any clinically significant findings during the visit and before the patient leaves the clinic. A qualified physician at a central diagnostic center will be interpreting the ECG.

All ECG results outside of the reference ranges will be judged by the investigator as belonging to one of the following categories:

- abnormal and not clinically significant
- abnormal and clinically significant

Any ECG finding that is judged by the investigator as clinically significant (except at the screening visit) will be considered an adverse event, recorded on the source documentation and in the CRF, and monitored as described in Section 7.1.2.

The criteria for an abnormal post-baseline QTcF are a value >500 msec or change from screening >60 msec. If one of these criteria is met, the investigator must further evaluate the QTcF as follows:

- If a standard ECG is abnormal and meets the above protocol criteria,
 - A 5-minute summary ECG recording should be performed at the research site, and a repeat standard ECG is not required. The site should follow the process to have these ECGs read by Spaulding.
 - If a 5-minute summary ECG cannot be performed (for instance, if patient is evaluated at a facility other than the research site, and the summary ECG is not available), the investigator should obtain 2 repeat standard ECGs and determine the average of these 3 post-screening QTcF values. The site should follow the process to have these ECGs read by Spaulding.
- The investigator should then compare the post-screening QTcF values to the pre-treatment QTcF values at screening. As noted above, the post-screening QTcF values will use either the average QTcF from the 3 post-screening standard ECGs or the QTcF from the summary ECG. The IMP must be stopped for any confirmed post-baseline QTcF average value >500 msec or average increase from screening >60 msec.

Note: Abnormal ECG results at week 3 and week 7 or at an unscheduled visit may result in patient withdrawal from the study as detailed in Section 4.3.

7.9. Assessment of Suicidality

TEV-50717 is considered to be central nervous system-active. In addition, there have been some reports of suicidal ideation or behavior as reported in the product label when it has been given to some patients with certain conditions. The sponsor considers it important to monitor for such events before and during this clinical study.

Some central nervous system-active IMPs may be associated with an increased risk of suicidal ideation or behavior when given to some patients with certain conditions. Although this IMP or other similar medicinal products in this class have not been shown to be associated with an increased risk of suicidal thinking or behavior when given to this study population, the sponsor considers it important to monitor for such events before or during this clinical study.

The study population being administered with TEV-50717 should be monitored appropriately and observed closely for suicidal ideation and behavior or any other unusual changes in

behavior. Consideration should be given to discontinuing TEV-50717 in patients who experience signs of suicidal ideation or behavior.

Families and caregivers of patients being treated with TEV-50717 should be instructed to monitor patients for the emergence of unusual changes in behavior, as well as the emergence of suicidal ideation and behavior, and to report such symptoms immediately to the study investigator.

Baseline assessment of suicidal ideation and behavior and treatment-emergent suicidal ideation and behavior will be assessed during the study using the children's C-SSRS described in Section 7.2.

Patients with a positive children's C-SSRS suicidal ideation score on either items 1 or 2 must be 1) discussed with the study medical monitor, 2) re-evaluated within 2 to 3 days in a clinic visit, and 3) treated according to the investigator's medical judgment. Consultation with a child/adolescent psychiatrist or licensed child/adolescent mental health provider is advised, followed by close ongoing monitoring.

If patients endorse or report a children's C-SSRS suicidal ideation score of 3, 4, or 5, the patients will be evaluated immediately by the investigator and referred for psychiatric evaluation. The medical monitor will be immediately consulted. If it is determined by the investigator, the medical monitor, and consulting psychiatrist that exposure to the IMP may have contributed to a change in children's C-SSRS and/or increased depressive symptoms, study medication will be immediately discontinued and the patient will be terminated from the study. In cases where it is determined that IMP did not contribute to changes in depression or suicidality, the investigator will consult with the medical monitor, consulting psychiatrist, and/or sponsor to determine whether the patient should continue in the study.

If patients report any suicidal behavior that is an actual attempt as assessed in the children's C-SSRS, they will be evaluated immediately by the investigator, referred for psychiatric evaluation, and terminated from the study.

If patients report any suicidal behavior that is interrupted, aborted, or preparatory as assessed in the children's C-SSRS, they will be evaluated immediately by the investigator and referred for psychiatric evaluation. In cases where it is determined in the psychiatric evaluation that IMP did not contribute to changes in suicidal behavior, the investigator will consult with the medical monitor, consulting psychiatrist, and/or sponsor to determine whether the patient should continue in the study.

7.10. Assessment of Depression

Families and caregivers of patients are instructed to monitor the patients for any changes in or new onset of depressive symptoms and unusual changes in mood, cognition, or behavior, and to report such symptoms immediately to the investigator. Telephone contacts (with non-recording live video) and clinic visits also allow opportunities for the investigator to assess adverse events.

If a relevant change in status is identified, patients will be seen immediately for an unscheduled visit by the investigator and discussed with the medical monitor. The patient will be referred for further psychiatric evaluation if there is any suspicion of experiencing depression. The investigator will record these symptoms as an adverse event of depression. If it is determined by

the investigator, after consultation with the medical monitor and consulting psychiatrist, that exposure to the IMP may have contributed to the adverse event of depression, study medication will be immediately discontinued and the patient will be terminated from the study. Follow-up with a pediatric psychiatrist or licensed child/adolescent mental health provider will be arranged.

In cases where it is determined that IMP did not contribute to the adverse event of depression, the investigator will consult with the medical monitor and/or sponsor to determine whether the patient should continue in the study.

7.11. Neurological Examinations

Neurological examination, including mental status, cranial nerves, motor system (strength, tone, and posture), coordination, gait and balance, tendon reflexes, and sensation, will be performed at the time points detailed in [Table 3](#). Any neurological examination finding that is judged by the investigator as a potentially clinically significant change (worsening) compared with the baseline value will be considered an adverse event, recorded on the CRF, and monitored as described in [Section 7.1.2](#).

7.12. Concomitant Medication or Treatment

Concomitant therapy or medication usage will be monitored throughout the study according to time points detailed in [Table 3](#). Parents/patients will be instructed during the course of the study to notify the investigator if any new medication is prescribed/administered (other than TEV-50717) or if there is any change in current medications, including over-the-counter medications. Any new prescribed/administered medication and/or any change in current prescribed/administered medication should be reviewed with the investigator.

Patients may be included in this study if they are using cannabis or formulations or derivatives of cannabis in relatively stable amounts, for medical purposes (where applicable according to local regulation), under the guidance, supervision, or prescription of a clinician and anticipated to remain stable (dose and frequency) within the study duration. Patients who are either using cannabis or its derivatives or formulations or patients who have a positive drug screen for cannabis or its derivatives or formulations can be submitted to the medical monitor for consideration of participation in this study. Patients with a substance use disorder are excluded from this clinical trial. If per the investigator's judgment, however, a patient does not meet the criteria for substance use disorder, a positive drug screen for cannabis or its metabolites, without medical explanation, will be discussed on a case-by-case basis between the research site, the Medical Monitor, and the sponsor to determine the patient's eligibility, based on the information available. Patients should be advised that the recreational use of cannabis or its derivatives or formulations should be avoided during this study.

Medications that are allowed, provided that conditions outlined in the table are met, are shown in [Appendix H, Table 10](#). Certain considerations mentioned in the table require the review of the medical monitor. Changes to the allowed medications may be permitted in the context of this study and should be discussed with the medical monitor. If the wellbeing of the patient and the urgency of the clinical decision do not allow discussion with the medical monitor prior to the medication change, the investigator should notify the medical monitor in a timely manner following this decision.

The medical monitor must be contacted if a patient is receiving (or has to begin or stop receiving during the study) a medication that is associated with QT prolongation or that is a known strong CYP2D6 inhibitor. Prohibited medications that are associated with QT prolongation are listed in Appendix H, [Table 11](#).

7.13. Methods and Time Points of Assessing, Recording, and Analyzing Safety Data

All adverse events will be reviewed on a periodic basis by the clinical project physician/medical monitor according to the safety monitoring plan (eg, scheduled safety reviews for TEV-50717) as preliminary safety databases become available. In addition, the iDMC will perform the unblinded IA and take part in safety monitoring throughout the study.

Methods and time points of assessing safety data are discussed in [Section 3.4](#). Procedures for recording safety data are discussed in [Appendix K](#), and methods of analyses are discussed in [Section 9.8](#).

8. ASSESSMENT OF PHARMACOKINETICS/ PHARMACODYNAMICS AND PHARMACOGENETICS

8.1. Pharmacokinetic Assessment

[REDACTED]

[REDACTED]

[REDACTED]

[REDACTED]

Table 9: Blood Sampling Scenarios

Scenario	Action
[REDACTED]	[REDACTED]
[REDACTED]	[REDACTED]
[REDACTED]	[REDACTED]
[REDACTED]	[REDACTED]

[REDACTED]

[REDACTED]

8.2. Assessment of Exploratory Biomarkers

[REDACTED]

8.3. Pharmacogenetics

8.3.1. CYP2D6 Genotyping/Pharmacogenetics

At the screening visit, a mandatory blood sample (3.0 to 5.0 mL) will be obtained for analysis of CYP2D6 genotype from all patients in the study at the time point detailed in [Table 3](#). The CYP2D6 genotype results will be provided to the RTSM, which drives each patient’s dose regimen, and the patient’s genotype for CYP2D6 will remain blinded during the conduct of the study.

[REDACTED]

9. STATISTICS

This section describes the statistical analysis as foreseen at the time of planning the study. Changes, additions, and further details about the analyses will be described in the statistical analysis plan (SAP). After finalization of the SAP, any additional analyses or changes to analyses that may be required will be fully disclosed in the CSR.

For COVID-19 updates, refer to [Appendix M](#).

9.1. Sample Size and Power Considerations

The initial sample size estimation of approximately 185 patients randomized to TEV-50717 versus placebo in a 2:1 ratio (approximately 124 in the TEV-50717 group; approximately 61 in the placebo group) is the sample size required to obtain a statistically significant result in the primary analysis based on a 1-sided test for mean difference at a significance level of $\alpha=0.025$ with a power of approximately 90%, assuming a mean difference of 1.8 and a standard deviation (SD) of 3.5 in each treatment group.

At the time of writing Amendment 05, the initially planned sample size has been reduced to approximately 65 patients randomized to TEV-50717 versus placebo in a 2:1 ratio (approximately 43 in the TEV-50717 group; approximately 22 in the placebo group).

The initial assumptions regarding the mean difference and SD are based on the change from baseline to month 6 in patients treated with trihexyphenidyl reported by [Battini et al \(2014\)](#), assuming an effect size of 55% for TEV-50717 versus placebo. The effect size of 55% was assumed based on the observed effect sizes of TEV-50717 in the pivotal studies in HD and TD. In the current study, these assumptions correspond to a mean difference of 2.0 in MD-CRS part II total score and an SD of 3.5 in each treatment group.

The rate of missing not at random (MNAR) data for the primary analysis is expected to be 10%. MNAR data will be imputed in a conservative manner as if they were obtained from patients in the placebo treatment group, regardless of the actual treatment group. As a result, the mean difference is expected to be reduced from 2.0 to 1.8 in the primary analysis. The impact of the missing data imputation on the SD is negligible.

9.2. Analysis Sets

9.2.1. Intent-to-Treat Analysis Set

The intent-to-treat (ITT) analysis set will include all randomized patients.

In the ITT analysis set, treatment will be assigned based on the treatment to which patients were randomized, regardless of which treatment they actually received.

For patients who discontinue the study and re-enter it (repeating the study from baseline), only the data from the repeated participation will be included in the ITT analysis set.

9.2.2. Modified Intent-to-Treat Analysis Set

The modified intent-to-treat (mITT) analysis set is a subset of the ITT analysis set including all randomized patients with at least 1 post-baseline centrally read MD-CRS part II assessment.

In the mITT analysis set, treatment will be assigned based on the treatment to which patients were randomized, regardless of which treatment they actually received.

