The primary estimand assesses the effectiveness in the reduction of choreiform movements in patients with DCP with predominant choreiform movement disorder, evaluated by the central reviewers, focusing on the causal effects attributable to the IMP. The secondary estimands assess the effectiveness on patients' ability to perform daily functions, the improvement in dyskinesia evaluated by the caregiver and the investigator, and the reduction in chorea and dystonia evaluated by the central reviewers, all with a focus on the causal effects attributable to the IMP.

The patient population for this study is patients with DCP with predominant choreiform movement disorder and severity of DCP represented by MD-CRS part II total score of ≥ 10 and CGI-S ≥ 4 at baseline. This population is expected to have the sensitivity to demonstrate clinically meaningful improvement following treatment with TEV-50717. Due to practical reasons, it is not possible to obtain a central reading of MD-CRS part II items at the time of the baseline visit prior to randomization; therefore, inclusion of a subject into the study is based on investigator scoring of MD-CRS part II items at baseline.

Analysis of Primary Endpoint:

The primary endpoint is the change from baseline to week 15 in centrally read MD-CRS part II total score (TEV-50717 versus placebo). The MD-CRS part II total score is obtained by summing the total raw scores of MD-CRS part II items (0 to 28).

The modified intent-to treat (mITT) analysis set (all randomized patients with at least 1 post-baseline centrally read MD-CRS part II assessment) will be used for the primary analysis.

The primary analysis will be a mixed-model, repeated-measures with the change in MD-CRS part II total score as the dependent variable. The model will include fixed effects for treatment

group, week (3 levels: weeks 9, 12, and 15), and treatment group by week interaction. The baseline MD-CRS part II total score, age group at baseline (2 levels: 6 to <12 years; 12 through 18 years, inclusive), and region (US; non-US) will be included as covariates. The unstructured covariance model will be used.

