At the time of informed consent, the parent/legally accepted representative will be counseled that, once randomized to treatment, patients are to remain in the study and complete all study procedures unless the choice is made to withdraw consent. Patients who withdraw from the study before completing the 15-week treatment period should have an early termination (ET) visit as soon as possible after the last dose of IMP. All patients who discontinue early will have a follow-up telephone contact for safety evaluation 2 weeks after ET; evaluations will be as described for week 17.

Patients who screen fail or terminate early from the study due to emergency circumstances (such as coronavirus disease 2019 [COVID-19]) may be allowed to re-screen/re-enter (respectively) the study at a later date, depending on the circumstances. Each case should be referred to the medical monitor and approved in advance.

[figure not shown]
There is a separate protocol for the open-label safety extension Study TV50717-CNS-30081.

The end of study is defined as last visit of the last patient.

The study schematic diagram is presented in [Figure 1](#).

For coronavirus disease 2019 (COVID-19) updates, refer to [Appendix M](#).

Figure 1: Overall Study Schematic Diagram

AE=adverse event; CGI=Clinical Global Impression; CYP2D6=cytochrome P450 2D6; ET=early termination; max=maximum.

Note: If a patient is CYP2D6-impaired, the dose administered is indicated in parentheses. The dose of the IMP should be increased on a weekly basis until any of the following events occur: clinically meaningful reduction in dyskinesia (ie, CGI-I) as determined by the investigator, clinically significant AE, or the maximum allowable dose is reached after remote or in-clinic visits.

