The MD-CRS part II will be administered by the investigational center physician, or other appropriately trained study team member, and video-recorded at screening, baseline, week 9, week 12, week 15/ET, and week 16/EOS visits.

The MD-CRS has been updated to version 2 with changes to the scoring language. This version should be used when available. However, a patient will complete all study visits using the same version.

Assessment of MD-CRS part II items will be based solely on chorea in this study and performed as follows:

- Local assessment (all time points): the investigational center physician will administer the MD-CRS part II and complete the assessment of item scores. Note: the physicians will receive training on MD-CRS scoring prior to the study.
- EAB review (screening): EAB will review the MD-CRS part II at the screening visit to confirm that dyskinesia severity is aligned with the protocol criteria for inclusion into the study. The review will include determination of the predominant dyskinesia type and scoring of MD-CRS part II items. The EAB will inform the site prior to the baseline visit if there are any discrepancies between the local and central assessments, and offer to discuss with the investigator. Ultimately, it is the investigator who determines the patient's eligibility. EAB assessment of screening MD-CRS part II total score will not be included in the statistical analysis.
- Central reading (baseline, week 9, week 12, week 15/ET, and week 16/EOS): Video review of MD-CRS part II will be assessed periodically in a blinded manner (ie, visit, investigator site rating, and other study-related information) by a central review board. Central reading results performed by the central raters, who are also the EAB members, will not be disclosed to the investigational site. Central reading details will be provided in a separate charter.

The primary efficacy endpoint is the change from baseline to week 15 in the MD-CRS part II total score (TEV-50717 versus placebo), assessed by central reading.

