9.3. Data Handling Conventions

9.3.1. Handling Withdrawals and Missing Data

For this study design and population, it is unlikely that patients who withdraw from IMP will be willing to attend the remaining scheduled study visits and, in particular, the week 15 visit. Therefore, patients will not be required to return to the clinic at week 15 for efficacy evaluations, and the primary analysis will be based on a multiple imputation method for missing data.

For efficacy analysis, missing data will be classified as missing at random (MAR) and MNAR. The following cases will be considered as MNAR:

- early terminations related to tolerability
- treatment-related adverse events
- early terminations related to lack of efficacy

The following cases will be considered as MAR:

- intermittent missing data
- early termination for patients who are lost to follow-up
- early terminations due to COVID-19

For all other cases, and for cases classified as above, classification as MAR/MNAR will be done/revisited in a blinded manner on a case-by-case basis prior to the IA for futility and prior to database lock for final analysis.

Multiple imputation methods will be used in the primary and secondary efficacy analyses. See Section 9.5 for details.

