9.5.2.2. Sensitivity Analysis

To assess the robustness of the primary efficacy analysis, sensitivity analyses will include the following:

Sensitivity analyses for assumptions of missing data mechanism:

- tipping point (MNAR)
- MAR multiple imputation

Sensitivity analysis for the statistical model:

- analysis of covariance (ANCOVA)
- primary model, including only the following covariates: treatment group, week, and treatment group by week interaction

Other:

- primary model repeated for the ITT analysis set
- primary model repeated for the set of patients in the mITT analysis set that received at least 1 dose of IMP
- primary model repeated for the PP analysis set
- ANCOVA models for MD-CRS part II total score change from baseline to week 9 and to week 12

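### The mITT primary set drops randomised patients who stop before week 9 and have no early-termination or unscheduled central read, although the estimand and the imputation rules cover them

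*Protocol*

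**What the plan says.** - **Primary set.** Section 9.2.2 defines mITT as a subset of ITT, "including all randomized patients with at least 1 post-baseline centrally read MD-CRS part II assessment". The synopsis (Analysis of Primary Endpoint) states its use: "all randomized patients with at least 1 post-baseline centrally read MD-CRS part II assessment) will be used for the primary analysis". Section 9.5.2.1 describes the model without naming a set.
- **When the scale is read.** Section 6.1 has MD-CRS part II "video-recorded at screening, baseline, week 9, week 12, week 15/ET, and week 16/EOS visits", and lists "Central reading (baseline, week 9, week 12, week 15/ET, and week 16/EOS". Nothing is scheduled at weeks 1 to 7. Table 3 also permits a central read at an unscheduled visit, at the investigator's discretion.
- **Early termination.** Under Section 3.1, patients who withdraw before completing treatment "should have an early termination (ET) visit as soon as possible after the last dose of IMP". Section 4.3 also asks for all assessments on the last day of study drug or soon after.
- **Estimand.** Section 9.5.1 defines the effect whether or not the dose was reduced, suspended or stopped.
- **Imputation.** Sections 9.3.1 and 9.5.2.1 class terminations for tolerability or lack of efficacy as missing not at random (MNAR), imputed by jump-to-reference. Loss to follow-up and COVID-19 terminations are missing at random (MAR), imputed from the randomised arm.
- **Sensitivity.** Section 9.5.2.2 lists "primary model repeated for the ITT analysis set".

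**The concern.** Entry to the confirmatory set depends on something that happens after randomisation. A patient who stops during the 7-week titration gets in only through an ET or unscheduled read, and the ET visit is something that should happen, not something assured. Those who miss it are removed before the imputation rules can act on them.

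The protocol itself describes routes to having no read. Appendix G defines loss to follow-up as repeated failure to return together with failed contact. Appendix M terminates patients who cannot complete the week 3 or week 7 safety assessments in reasonable time, and makes MD-CRS optional at remote visits. Section 9.3.1 says that both kinds of termination are to be imputed.

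Two things are at stake. First, the comparison is no longer strictly of the groups as randomised, in the test that gates all five key secondary endpoints (Section 9.6). Second, where an excluded patient would have been imputed by jump-to-reference, the exclusion moves the expected difference towards the active arm.

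The key secondaries may be affected too. Section 9.5.4.1 analyses CaGI-I and CGI-I in the same way as the primary endpoint, changing only the covariate and the weeks (3, 7, 9, 12 and 15). If the set carries over, a patient with week 3 or week 7 scores but no MD-CRS read is dropped despite having data on that endpoint.

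**Working it through.** **Inputs.** From Section 9.1: true difference 2.0, planned difference 1.8, SD 3.5, MNAR rate 10%, initial allocation 124:61, current allocation 43:22, one-sided alpha 0.025. Two assumptions are added. The 10% is taken as a share q of all randomised patients. The share f of those patients with no post-baseline central read is not in the protocol and is varied from 0 to 1.

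**Reproducing the plan's figures.**
- Dilution: 2.0 × (1 − 0.10) = 1.8, as stated.
- Power at 124:61: the standard error is 3.5 × √(1/124 + 1/61) = 0.547. Then 1.8/0.547 − 1.96 = 1.33, which gives power 0.908 against the stated 90% or so. The normal approximation needs 180 patients for 90%, close to 185.

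**Target under each set.** Under jump-to-reference an MNAR patient on active contributes an expected difference of 0, and every other active patient contributes 2.0.
- ITT: 2.0 × (1 − q) = 1.80.
- mITT: a fraction f·q leaves, so the target is 2.0 × (1 − q)/(1 − f·q).

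**Results at 43:22 and q = 0.10.** The standard error is 3.5 × √(1/43 + 1/22) = 0.92. The number excluded is 65 × 0.10 × f, assuming equal rates in both arms.

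| f (assumed) | Excluded | mITT target | Excess over 1.80 | Excess / SE |
|---|---|---|---|---|
| 0 | 0 | 1.80 | 0 | 0 |
| 0.25 | 1.6 | 1.8/0.975 = 1.85 | 0.05 (3%) | 0.05 |
| 0.5 | 3.2 | 1.8/0.95 = 1.89 | 0.09 (5%) | 0.10 |
| 1 | 6.5 | 1.8/0.90 = 2.00 | 0.20 (11%) | 0.22 |

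Power at this sample size runs from 0.50 (f = 0) to 0.54 (f = 1), so the choice of set barely changes it.

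**MAR patients.** These are imputed from their own arm. Under that model their expected contribution equals that of the patients who remain, so excluding them does not shift the expected difference. The shift above comes only from MNAR patients with no read.

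**The case against.** The strongest defence is that the ET visit closes most of the gap. MD-CRS part II is recorded and centrally read there, and Section 9.2.2 accepts any post-baseline central read, not only weeks 9, 12 or 15. A drop-out who attends ET with a readable video is in mITT and has the later visits imputed. This stands. A reader might infer from the week 9 start that titration drop-outs leave the primary set as a class; the documents do not support that.

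Other tempting inferences also fail:
- Section 9.3.1 says "it is unlikely that patients who withdraw from IMP will be willing to attend the remaining scheduled study visits", in particular week 15. That concerns continued follow-up. It does not predict missed ET visits.
- No section says when tolerability drop-out is most likely.
- Section 9.1 says "The rate of missing not at random (MNAR) data for the primary analysis is expected to be 10" percent. A reader might see a contradiction with mITT, because 1.8 requires those patients to be analysed. That follows only if the 10% is a share of all randomised patients. Read as a rate within the mITT set, 1.8 is simply the mITT expectation.
- Doubling the MNAR rate to 20% with no reads at all would give 2.0 against 1.6, or +25%. Neither input is in the protocol.

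The patients most clearly at risk of having no read, those lost to follow-up or terminated for COVID-19, are classed as MAR, for which no expected shift arises. COVID-19 terminations may also re-enter, and Section 9.2.1 then uses the repeat data. Finally, the ITT repeat is pre-specified, so a divergence would be visible.

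That last point lowers the severity but does not remove the defect. A sensitivity analysis neither supplies the confirmatory p-value nor opens the gate to the key secondaries.

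**Conclusion.** The point holds in a limited form. A randomised patient who stops before week 9 and has no ET or unscheduled central read is excluded from the primary analysis, against the estimand and the imputation rules. The exclusion serves no evident technical need, because the protocol already plans the same model on all randomised patients.

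The size is 0 to +11% on the expected difference (1.80 to 2.00), or 0 to about 0.2 of a standard error. This rests on a true difference of 2.0, on 10% of all randomised patients being MNAR, and on an unknown share without a read. If every drop-out has an ET read, there is no effect. The upper end requires that no MNAR patient has any read, including those who stop after week 9, so it is a bound and not an expectation.

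Severity is moderate. The case for change rests on keeping the confirmatory comparison as randomised and in line with its own estimand, more than on the likely numerical shift.

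**What to change.** Name ITT (all randomised patients, analysed as randomised) as the primary set in the synopsis and Section 9.5.2.1, and relabel mITT in Section 9.2.2 as a sensitivity set. State that patients with no post-baseline read are imputed from baseline under the same MAR or jump-to-reference rule as everyone else. Say explicitly in Section 9.5.4.1 that ITT also applies to the key secondary endpoints. In Section 9.5.2.2, replace the ITT repeat with an mITT repeat.

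This swaps two analyses that are already planned, so the cost is wording in the protocol and matching text in the SAP. The estimate may come out slightly less favourable to the active arm.
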